Descriptive statistics (N, mean, standard deviation, median, minimum, and maximum) will be presented for continuous variables. Geometric means and coefficient of variation will also be presented for PK data. Frequency distributions (counts and associated percentages) will be presented for categorical variables. Median, 25th and 75th percentiles and confidence intervals (Cls) will be presented for time-to-event data. Unless specified otherwise, CIs will be presented as 95% Cls.

The study is descriptive in nature and is not powered for a confirmatory statistical goal or objective. Formal hypothesis testing will not be done, and no adjustment for multiple comparisons will be used.

Individual patient data listings will be provided to support summary tables.

Version: Amendment 4 Date: 31 Mar 2020

The effects of noncompliance, treatment discontinuations, premature study withdrawals, subsequent therapies, and covariates will be assessed to

determine the impact on the general applicability of results from this study.

Protocol Number: NVGN-0084-201

IND Number: 112,608

Analysis of Clinical Benefit:

The Kaplan-Meier method will be used to describe and present PFS and any other time-to-event endpoints (OS, TTP, etc). Median PFS will be presented with 95% CI, 25th and 75th percentiles and minimum and maximum values. Kaplan-Meier estimates of PFS at 6, 9, and 12 months will also be presented with 95% CIs.

The primary analysis of time to event endpoints (OS, TTP, and PFS) from Stage 2 will be based on the mITT and/or PP as appropriate.

For exploratory analyses, DCR will be compared between treatment arms using Fisher's exact test. The difference in the proportion of responders and corresponding 95% CI (based on the Hauck-Anderson approach) will also be displayed. The blinded central review disease response assessments will be used as the primary measure for analysis, and the Investigator disease response assessments will be used as supportive measures for analysis.

Safety Analysis:

All safety analyses will be conducted in the safety population.

AEs will be coded according to the Medical Dictionary for Regulatory Activities (MedDRA). The severity of AEs will be graded according to the United States NCI CTCAE, version 4.03.

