The randomized clinical trial EORTC (European Organization for Research and Treatment of Cancer) 26981-22981/NCIC CTG (National Cancer Institute of Canada Clinical Trials Group) CE.3 established TMZ as part of the standard of care for GBM. It has long been established, however, that GBM patients with a methylated MGMT promoter (epigenetically silenced) are most likely to benefit from the addition of TMZ as an adjuvant therapy following combined XRT/TMZ (Hegi, Diserens et al. 2005, Stupp, Hegi et al. 2009). Patients with unmethylated MGMT promoter tumors derived only a 1-month improvement in median survival, and absolute increases in 2- and 5-year survival of approximately 13% and 8%, respectively (Hegi, Diserens et al. 2005, Stupp, Hegi et al. 2009). The marginal benefit of combination therapy for the unmethylated population has brought into question the use of combination therapy as an absolute standard, particularly in the clinical trial setting (Alexander and Cloughesy 2017). While the Stupp regimen (Stupp, Mason et al. 2005) has been the standard of care in adjuvant and newly diagnosed GBM for over a decade, data have shown that OS in the two-thirds of patients who have unmethylated MGMT is only 12.7 months, and PFS is only 5.3 months (Hegi, Diserens et al. 2005).

Patients with unmethylated MGMT, therefore, represent the patient group with the highest unmet need requiring new treatment options; a role that GDC-0084 may fulfil given that its action is independent of the MGMT promoter status of GBM tumors.

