4.2 Eligibility Criteria

4.2.1 **Inclusion Criteria**

Patients must meet all the following inclusion criteria to be eligible for enrollment into the study:

- 1) Signed informed consent approved by the Institutional Review Board (IRB). Patients must sign an authorization for the release of their protected health information;
- 2) Age ≥ 18 years;
- 3) Life expectancy > 12 weeks;
- 4) Present with histologically confirmed intracranial (supratentorial) unmethylated MGMT promotor status GBM (WHO Grade IV astrocytoma) with an MGMT status that has been confirmed by validated PCR or validated alternative genomic analysis;
- 5) Have undergone maximal or subtotal surgical resection of their tumor and within 6 weeks of surgery commenced radiation and then received at least 75% of planned treatment with XRT/TMZ or XRT only (if clinically indicated), which consists of XRT by external beam to a partial brain field in daily fractions of 2.0 Gray (Gy), to a planned total dose to the tumor of 60.0 Gy, in conjunction with TMZ oral QD 75 mg/m² in accordance with the Stupp regimen;
- 6) Karnofsky Performance Status (KPS) ≥ 70;
- 7) Cranial magnetic resonance imaging (MRI) must have been performed within 14 days prior to or on the day of the Enrollment/Week 1 Visit;
- 8) Stable or decreasing corticosteroid dose within 7 days prior to the first dose;
- 9) Adequate bone marrow/hematological function within 14 days prior to Day 1:
 - White blood cell count (WBC) > 3,000/µL, absolute neutrophil count > 1,500/mm³;
 - Platelet count of > 100,000/mm³;
 - Hemoglobin > 10 mg/dL;
 - Eligibility level for hemoglobin may be reached by transfusion;
- 10) Adequate liver function within 14 days prior to Day 1:
 - Total bilirubin ≤ 1.5 x ULN;
 - AST and ALT ≤ 2.5 x ULN;
- 11) Adequate renal function within 14 days prior to Enrollment/Week 1 Visit:
 - Creatinine ≤ 1.5 mg/dL;
 - Urine dipstick for proteinuria < 2+. Patients discovered to have ≥ 2+ proteinuria on dipstick urinalysis should undergo a 24-hour urine collection and must demonstrate ≤ 1.0 g of protein in 24 hours: OR
 - Urine protein/creatinine ratio ≤ 1.0;
- 12) International normalized ratio (INR) or prothrombin time (PT) (secs) and activated partial thromboplastin time (aPTT) within 7 days prior to Enrollment:
 - ≤1.5 x ULN (except for patients receiving anticoagulation therapy) in the absence of therapeutic intent to anti-coagulate the patient;

Version: Amendment 4 Date: 31 Mar 2020

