6.3.1 Analysis Populations

The following analysis populations are defined:

- The Intent -to-Treat (ITT) population includes all randomized patients; ITT analyses will be conducted on the basis of the arm assigned at randomization
- The Modified Intent-to-Treat (mITT) population includes allI eligible patients who received at least 1 dose of GDC-0084 and have evaluable post-baseline tumor response data; mITT analyses will be conducted on the basis of the treatment assigned at randomization;
- Safety population (SAF): All eligible patients who received at least 1 dose of GDC 0084 will be included in the safety population. Safety analyses will be conducted on the basis of initial received treatment;
- PK population: All eligible patients in the safety population who have an adequate concentration vs. time profile to determine PK parameters
- A Per-Protocol (PP) subset will also be used to analyze endpoints of clinical benefit and will be based on study drug exposure (compliance and/or time on study drug) and major protocol deviations. The criteria for inclusion in the PP subset will be finalized and documented prior to database lock.

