PFS is defined as the time in months from start date and/or date of disease diagnosis until disease progression or death due to any cause. Patients without disease progression or death will be censored at the last evaluable radiographic assessment. Patients with no post-dose radiographic assessment will be censored at their start date (Day 1). The primary analysis of PFS will be conducted in the SAF for Stage 1 and the mITT for Stage 2. Analyses of PFS may be repeated in the PP.

The Kaplan-Meier method will be used to describe and present PFS. Median PFS will be presented with 95% CI, 25th and 75th percentiles and minimum and maximum values. Kaplan-Meier estimates of PFS at 6, 9, and 12 months will also be presented with 95% CIs. PFS will also be displayed graphically using Kaplan-Meier estimates.

For Stage 2, differences between treatment arms will be tested using a two-sided log rank test. Stratified hazard ratio (HR) estimates of the treatment comparisons with associated 95% CIs will be estimated from a Cox regression model.

OS is defined as the time in months from start date and/or disease diagnosis until death due to any cause. Patients who are alive at the time of analysis will be censored at the date last known to be alive. The primary analysis of PFS will be conducted in the SAF for Stage 1 and the ITT for Stage 2. Analyses of OS may be repeated in the mITT and/or PP.

TTP is defined as the time in months from start date and/or until disease progression . Patients without disease progression will be censored at the last evaluable radiographic assessment. Patients with no post-dose radiographic assessment will be censored at their start date (Day 1).

Analyses of OS and TTP will be performed using the same methods as described for PFS.

Post-hoc stratification/analysis factors may include disease progression (post-surgery at time of baseline visit) and baseline KPS.

Version: Amendment 4 Date: 31 Mar 2020

Protocol Number: NVGN-0084-201

IND Number: 112.608

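### Stage 2 primary PFS is set in the mITT, which leaves out treated patients who die before any evaluable post-baseline tumor assessment, although death is a PFS event

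*Combined protocol and SAP*

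**What the plan says.** **Event and population.** Section 4.5.2 measures Stage 2 PFS from randomization to RANO progression or death from any cause. Section 6.3.4 also counts any death as an event, then sets the population: "The primary analysis of PFS will be conducted in the SAF for Stage 1 and the mITT for Stage 2". Section 6.3.1 limits the mITT to eligible "patients who received at least 1 dose of GDC-0084 and have evaluable post-baseline tumor response data". The only repeat named for PFS is an optional one in the per-protocol subset. The ITT is defined in section 6.3.1 as every randomized patient, but the PFS paragraph does not use it.

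**Imaging.** Section 4.6.3 schedules the first post-baseline MRI at Week 8 and then every 8 weeks. Table 1 adds an MRI at the End of Treatment visit.

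**Censoring.** Section 6.3.4 gives two rules in sequence: "Patients without disease progression or death will be censored at the last evaluable radiographic assessment" and "Patients with no post-dose radiographic assessment will be censored at their start date (Day 1".

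**Other population statements.** The OS paragraph of section 6.3.4 says "The primary analysis of PFS will be conducted in the SAF for Stage 1 and the ITT for Stage 2", and its next sentence allows OS to be repeated in the mITT and per-protocol sets. The synopsis says that the Stage 2 primary analysis of OS, TTP and PFS "will be based on the mITT and/or PP as appropriate".

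**The concern.** Entry to the primary PFS set depends on something that happens after randomization, namely surviving and staying on study long enough to have an evaluable assessment. The events most exposed to removal are the earliest deaths. Progressions documented on MRI are not exposed, because they come with a scan.

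Removing early deaths raises the Kaplan-Meier curve at every later time. The planned outputs in section 6.3.4 are the median and the 6-, 9- and 12-month estimates, and their confidence intervals do not reflect the removal. Stage 1 PFS uses the safety population, which has no tumor-data filter, so the two stages report PFS under different rules.

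A second, separate problem is that the body and the synopsis do not agree on the OS population.

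**Working it through.** The plan gives no power, event count or dropout figure for PFS, so it has no design figure for PFS to reproduce. The Stage 2 size is 20, randomized 1:1 (section 4.3.1). The rest is illustration under stated assumptions.

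**1. Path of an unscanned death**
- Endpoint definition: it is a PFS event.
- mITT definition: with no evaluable post-baseline data, the patient is excluded.
- Repeat analyses named for PFS: per-protocol only, which is not designed to restore the patient.
- Day 1 censoring rule: it applies to patients with no post-dose scan, who are mostly outside the mITT already. The two rules do not appear to have been reconciled.

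**2. How many patients might be affected**

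Section 3.2 cites historical figures for unmethylated MGMT: "OS in the two-thirds of patients who have unmethylated MGMT is only 12.7 months, and PFS is only 5.3 months". The time origin is not given. Assume exponential survival from entry.
- Week 8 = 56 / 30.44 = 1.84 months.
- P(death before Week 8) = 1 − exp(−ln 2 × 1.84 / 12.7) = 0.0955, or 1.9 of 20.
- For assumed medians of 10 and 16 months: 0.120 (2.4 of 20) and 0.0766 (1.5 of 20).

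These are upper-end figures. Section 4.2.1 requires "Life expectancy > 12 weeks", and some early deaths will follow an End of Treatment MRI. The share of these deaths with no evaluable assessment, f, is not in the documents. With the 12.7-month median:

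| f (assumed) | Expected loss, 20 × 0.0955 × f | P(at least one), 1 − (1 − 0.0955f)^20 |
|---|---|---|
| 0.25 | 0.48 | 38% |
| 0.50 | 0.96 | 62% |

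**3. Effect on PFS**

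Assume exponential PFS with a 5.3-month median. Then S(6) = exp(−ln 2 × 6 / 5.3) = 45.6%. If a fraction q of patients, all with early events, is removed, S(t) becomes S(t) / (1 − q), and the median becomes 5.3 × ln(2 / (1 − q)) / ln 2.

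| Removed | q | 6-month PFS | Median (months) |
|---|---|---|---|
| 0 of 20 | 0 | 45.6% | 5.3 |
| 1 of 20 | 0.05 | 48.0% | 5.7 |
| 2 of 20 (upper end) | 0.10 | 50.7% | 6.1 |

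For assumed PFS medians of 4 and 7 months, losing one of 20 moves 6-month PFS from 35.4% to 37.2% and from 55.2% to 58.1%.

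**4. Sampling error for scale**

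The half-width is 1.96 × √(0.456 × 0.544 / 20) = 0.218, about 22 points.

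**5. Why changing the population alone is not enough**

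A patient censored at time zero contributes nothing to a Kaplan-Meier estimate. If the Day 1 rule were applied literally to an unscanned death, the ITT curve would equal the curve with that patient removed. The population and the censoring sentence must therefore be corrected together.

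**The case against.** **Size and setting.** The shift from losing one patient is about 2.4 points against a half-width of about 22. It rests on an assumed unscanned share and a constant hazard from entry. PFS is secondary, section 6.3.3 calls the study descriptive, OS captures the same deaths, and patient listings are planned. All of this stands and limits the weight. It does not remove the selection, which for early deaths acts in one direction.

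**The SAP.** Section 6.3 gives missing-data handling to a separate, higher-level SAP, and section 6.3.4 leaves the effect of progression confirmation and related sensitivity analyses to it. That document was not supplied and may deal with this. Nothing supplied does.

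**Other exclusions.** An unscanned patient whose event falls after 6 months would move the estimate the other way: (45.6 − 5) / 0.95 = 42.8%. Such a patient would have missed the Week 8 MRI and any later or End of Treatment MRI, so this is the less likely case.

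Three stronger readings are tempting, and the documents do not support them:
- **That the plan contradicts itself on the PFS population.** The ITT sentence is in the OS paragraph and is followed by a sentence on repeating OS, so it is evidently a slip for OS. For PFS, the synopsis is looser than the body rather than clearly opposed to it. The real mismatch is for OS.
- **That early deaths are to be censored at Day 1.** The preceding sentence limits censoring to patients without progression or death, so an unscanned death is probably meant as an event. The rule needs clarifying.
- **That the fed/fasted hazard ratio would be badly distorted.** A large shift needs several such deaths in one arm. With a per-patient probability of 0.0239 or 0.0478 (0.0955 × f), two or more in a given arm of 10 has probability of about 2% or 8%. By section 4.4.1 the arms differ on only two dosing days, so this ratio carries little efficacy meaning.

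**Conclusion.** The point holds and should be fixed, at modest weight. As written, the Stage 2 primary PFS set leaves out treated patients who die before any evaluable assessment, and their removal raises median and landmark PFS. Under the assumptions above, the expected loss is about 0.5 to 1 of 20 patients. One loss adds about 2.4 points to 6-month PFS and 0.4 months to the median. The direction follows from the text; the size depends on an early-death count and an unscanned share that the documents do not give.

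Separately, the OS paragraph names the wrong endpoint, and once that is corrected to OS in the ITT, the synopsis contradicts it.

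**What to change.** - Make the ITT, already defined, the Stage 2 primary set for PFS, with the mITT and per-protocol analyses supportive.
- State that death before any post-baseline scan is a PFS event on the date of death. Limit Day 1 censoring to patients who are alive, without progression and without a scan.
- Use randomization as the Stage 2 time origin, as in section 4.5.2, in place of the section 6.3.4 wording that also allows a start date or the date of diagnosis. This matters for anyone randomized but never dosed.
- In the OS paragraph, replace PFS with OS, and bring the synopsis into line.
- Section 5.5 allows clinical progression to be determined from symptoms in rare cases. State whether such progression, documented without a scan, is an event for PFS and TTP. If it is, use the ITT for TTP too. Section 6.3.4 names no TTP population. If it is not, unscanned patients censored at Day 1 leave the TTP curve unchanged.
- Report mITT exclusions by arm with reasons, and carry the same wording into the SAP.

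The cost is protocol and SAP wording, with no new data collection. The PFS estimate may be slightly less favourable.

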4.5 Endpoints

4.5.1 **Primary Endpoint**

The primary endpoint of this study is safety-related and is the occurrence of DLTs during the study.

Protocol Number: NVGN-0084-201

Secondary Endpoints 4.5.2

Secondary endpoints are related to both, safety and clinical benefit as listed below.

Secondary Safety Endpoints:

- Treatment-emergent AEs (TEAEs), Grade 3-5 TEAEs, serious adverse events (SAEs), fatal AEs, and TEAEs leading to GDC 0084 discontinuation or study withdrawal;
- Treatment-emergent Grade 3/4 clinical laboratory abnormalities;
- Changes and shifts from baseline in clinical laboratory, vital signs, and ECG parameters;
- Change from baseline in corticosteroid use;
- Change from baseline in LVEF;
- Change from baseline in KPS;
- Concomitant medication use;
- Adherence to the dosing regimen.

Secondary Endpoints of Clinical Benefit:

- PFS measured from first dose in the dose-escalation portion (Stage 1) or from randomization in the cohort expansion portion of the study (Stage 2) to disease progression (RANO criteria) or death due to any cause:
- OS measured from first dose in the dose-escalation portion (Stage 1) or from randomization in the cohort expansion portion of the study (Stage 2) to death due to any cause;
- TTP measured from first dose in the dose-escalation portion (Stage 1) or from randomization in the cohort expansion portion of the study (Stage 2) to date of earliest disease progression according to RANO criteria.

4.5.3 **Exploratory Endpoints**

Exploratory endpoints in this study are:

- PFS measured from first dose in the dose-escalation portion (Stage 1) or from randomization in the cohort expansion portion of the study (Stage 2) to disease progression (modified RANO criteria) or death due to any cause:
- PK parameters including area under the curve from time 0 to last measurable time point (AUC_{0-last}) and/or area under the curve from time 0 to infinity (AUC_{0-inf}), maximum concentration (C_{max}), minimum concentration (C_{min}), time to reach C_{max} (T_{max}), t_{1/2}, apparent total clearance of the drug from plasma after oral administration (CL/F), and accumulation ratio for C_{max} and AUC (fed and fasted);
- Change in FDG-PET uptake in tumor and normal brain tissue (defined as normal brain tissue with similar cell type to tissue surrounding tumor) in response to GDC-0084 in patients with measurable disease:

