4.6.3 Radiographic Assessments

For all patients, an MRI of the brain will be performed; cranial MRI scan must have been performed within 14 days prior to or on the day of the Enrollment/Week 1 visit and then every 8 weeks starting at Week 8. The international standardized brain tumor imaging protocol will be followed for MRI imaging. Minimum sequences required are: 3D pre-contrast T1, T2/FLAIR, and 3D post-contrast T1. Slice thickness for 3D pre- and post-contrast T1 images should be ≤ 1.5 mm with no gap and slice thickness for 2D T2 and FLAIR should be ≤ 4 mm with no interslice gap.

For the expansion cohort, the assessment of disease progression will be done by MRI analysis according to RANO criteria. Evaluation will be conducted by a central radiography vendor using 2 central readers who are blind to treatment assignment (fed or fasted), with an adjudication process when there is disagreement between the 2 central readers.

Patients in Stage 2 with measurable disease, and subject to research site having capability, will be required to undergo FDG-PET imaging and analyses will be performed by accredited specialist facilities.

FDG-PET imaging will occur at Randomization/Week 1, Days 3 and 7 of Cycle 1. Timing and days of FDG-PET imaging may change on the basis of PK e.g. T_{max} and other data analyzed during the study. FDG-PET imaging may be obtained using a stand-alone PET or combined PET/computed tomography (CT) scanner, or hybrid PET/MRI systems.

The image acquisition system must remain consistent throughout all scans for the same patient. MRI imaging will be performed according to standardized procedures. The central review disease response assessments will be used as the primary measure for analysis, and the Investigator disease response assessments will be used as supportive measures for analysis.

At the Randomization/Week 1 visit, the baseline pre-treatment FDG-PET imaging must be performed prior to the pre-dose PK sample and the first intake of GDC-0084. Imaging should be completed at least 1 hour prior to pre-dose PK sampling. For logistical reasons, the pre-treatment FDG-PET may be performed up to 1 day prior to the Randomization/Week 1 visit.

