4.6.11 Unscheduled Visits

Unscheduled visits may be conducted at any time during the study by the Investigator if clinically indicated for the care of the patient. An unscheduled visit may include any of the protocol required assessments listed in Section 4.6. The exact assessments conducted at the unscheduled visit will be specified by the Investigator and recorded in the CRF. Additional tests and procedures may be performed at the unscheduled visit for the clinical care of the patient after discussion with, and agreement of, the medical monitor.

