5.5 Serious Adverse Events

An SAE is any untoward medical occurrence at any dose that:

- Results in death (when there is unmistakable evidence that death was due to a cause other than disease under study, otherwise death is report as a study endpoint);
- Is life-threatening (immediate risk of death);
- Requires inpatient hospitalization or prolongation of existing hospitalization;
- Results in persistent or significant disability/incapacity (substantial disruption of the ability to conduct normal life functions);
- Results in congenital anomaly/birth defect;
- Is determined to be an important medical event by the Investigator.

Progression of the malignancy under study (including signs and symptoms of progression) should not be reported as an SAE unless the outcome is fatal within the safety reporting period. Hospitalization

Date: 31 Mar 2020

Protocol Number: NVGN-0084-201 Version: Amendment 4 IND Number: 112.608

due to signs and symptoms of disease progression should not be reported as an SAE. Disease progression and death will be reported as part of the study endpoints and not as AEs or SAEs.

Events that are clearly consistent with the expected pattern of progression of GBM should not be recorded as AEs. These data will be captured as efficacy assessment data only. In most cases, the expected pattern of progression will be based on the RANO criteria. In rare cases, the determination of clinical progression will be based on symptomatic deterioration. However, every effort should be made to document progression using objective criteria. If there is any uncertainty as to whether an event is due to disease progression, it should be reported as an AE.

Medical and scientific judgment is exercised in determining whether an event is an important medical event. An important medical event may not be immediately life-threatening and/or result in death or hospitalization. However, if it is determined that the event may jeopardize the patient or may require intervention to prevent one of the other AE outcomes, the important medical event should be reported as serious.

Examples of such events are intensive treatment in an emergency room or at home for allergic bronchospasm; blood dyscrasias or convulsions that do not result in hospitalization; or development of drug dependency or drug abuse.

5.5.1 **Drug Induced Liver Injury**

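### The 9-month PFS landmark falls just before the Week 40 scan, so 9-month PFS is likely to read about 5 to 7 points too high

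*Combined protocol and SAP*

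**What the plan says.** Section 6.3.4 (Analysis of Clinical Benefit) and the synopsis both plan three landmark rates: "Kaplan-Meier estimates of PFS at 6, 9, and 12 months will also be presented with 95% CIs". On censoring, Section 6.3.4 says: "Patients without disease progression or death will be censored at the last evaluable radiographic assessment". A death counts as an event.

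Section 4.6.3 (Radiographic Assessments) requires a baseline MRI "and then every 8 weeks starting at Week 8". Table 1 gives the on-treatment 8-weekly visits a window of 3 days either side.

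The time origin is stated in two ways. Section 4.5.2 starts the PFS clock at first dose in Stage 1 and at randomization in Stage 2. Section 6.3.4 has: "PFS is defined as the time in months from start date and/or date of disease diagnosis until disease progression or death due to any cause".

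The supplied text does not tie the landmarks to the scan calendar, define a month in days, or plan an interval-censored analysis. Sections 6.3 and 6.3.4 leave data handling, rules for confirming progression and related sensitivity analyses to a separate SAP, which is not part of that text.

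**The concern.** Kaplan-Meier places a scan-detected progression on the date of the scan that shows it, so the curve for such events drops only at scans. A landmark just after a scan includes nearly all the progression that has occurred. A landmark just before a scan omits almost a full interval of it. Nine months is of the second kind, while six and twelve months fall 2 to 4 weeks after a scan.

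The error runs in one direction, and the printed confidence interval does not cover it. Both Stage 2 arms receive the study drug and share one scan calendar, so the comparison between arms is largely untouched. Single-agent activity, however, can be judged only against outside rates. A 9-month figure raised by the scan calendar would mislead if set beside a rate read on a different schedule.

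**Working it through.** The plan states no expected PFS rate, so there is no figure of its own to reproduce.

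**Inputs**
- Landmarks at 6, 9 and 12 months (Section 6.3.4).
- Scans every 56 days from Day 1 (Section 4.6.3), with 3 days either side (Table 1).
- Month = 30.4375 days (assumption; the plan gives none). Days are elapsed days from Day 1.
- Median PFS of 5.3 months, the only figure in the documents. Section 3.2 cites it for the historical regimen: "unmethylated MGMT is only 12.7 months, and PFS is only 5.3 months". It is not a planning value for this trial, so medians of 3 to 12 months are also shown.
- Exponential PFS (assumption): S(t) = 0.5^(t / median).

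**Step 1: calendar**

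| Landmark | Day | Last scan before | Next scan |
|---|---|---|---|
| 6 months | 182.6 | Week 24, Day 168 (5.52 months) | Week 32, Day 224 |
| 9 months | 273.9 | Week 32, Day 224 (7.36 months) | Week 40, Day 280 (window 277 to 283) |
| 12 months | 365.25 | Week 48, Day 336 (11.04 months) | Week 56, Day 392 |

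Nine months falls 280 − 273.9 = 6.1 days before the Week 40 scan, or 3.1 to 9.1 days with the window. With 30-day months it is Day 270, 10 days before.

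**Step 2: overstatement if every event is dated at a scheduled scan**

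Gap = S(last scan) − S(landmark). At a median of 5.3 months:
- 6 months: 48.6% − 45.6% = 3.0 points.
- 9 months: 0.5^(7.36/5.3) − 0.5^(9/5.3) = 38.2% − 30.8% = 7.4 points.
- 12 months: 23.6% − 20.8% = 2.8 points.

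A simulation of 400,000 patients with the 3-day window gives 3.0, 7.3 and 2.8.

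| Assumed median (months) | 3 | 4 | 5.3 | 6 | 7 | 8 | 10 | 12 |
|---|---|---|---|---|---|---|---|---|
| 9-month gap (points) | 5.8 | 6.9 | 7.4 | 7.4 | 7.2 | 7.0 | 6.5 | 5.9 |

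Over the same medians the gap is 2.0 to 3.1 points at 6 months and 1.6 to 3.1 at 12 months.

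**Step 3: some events carry their own dates**

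If a share f of events is dated exactly, the gap becomes (1 − f) × 7.38 points at a 5.3-month median: 6.6 at f = 10%, 5.9 at 20%, 5.2 at 30% and 3.7 at 50%.

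**Step 4: shape of the curve (5.3-month median, all events at scans)**

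The loss from 6 to 9 months would appear as 48.6 − 38.2 = 10.4 points and from 9 to 12 months as 38.2 − 23.6 = 14.6. The underlying losses are 45.6 − 30.8 = 14.8 and 30.8 − 20.8 = 10.0. The uneven gaps reverse the order.

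**Step 5: scale**

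Near a rate of 34.5%, the 95% half-width is 1.96 × √(0.345 × 0.655 / n): about 21 points at n = 20 and 29 at n = 10. The 7.4-point shift is about a third of the half-width at n = 20.

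**The case against.** **Not every event waits for a scheduled scan.** Deaths enter on their own date. Table 1 has an End of Treatment MRI, and Section 4.6.11 says: "An unscheduled visit may include any of the protocol required assessments listed in Section 4.6". Section 5.5 adds: "In rare cases, the determination of clinical progression will be based on symptomatic deterioration". This stands. A reader might infer that the 9-month figure is simply a 7.4-month figure, about 7 points too high. That holds only for scan-detected progression, and 7 points is near the upper end of a model-based range.

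**Week counting is not fixed.** Table 1 labels Day 1 as Week 1. If Week 8 began on Day 50, the Week 40 scan would come 273 days after Day 1 (8.97 months). The 9-month gap would then be about 0, or about 3 points with the scan window. The 28-day cycles and the 8-weekly column favour 56-day intervals but do not settle it. Off-treatment follow-up also has a 14-day window, which straddles the landmark.

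**The time origin is ambiguous.** If PFS ran from diagnosis, alignment would differ by patient. With an assumed 2 to 4 months from diagnosis to Day 1, the 9-month gap at a 5.3-month median runs from about 3 to 13 points. That origin does not cure the problem.

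**The separate SAP may deal with it.** It may, and Section 6.3 ranks it above this text. The matters expressly left to it do not change the landmarks and method already stated.

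**Little depends on it.** PFS is a secondary endpoint in a descriptive study, no decision rule uses these rates, and sampling error is larger. This limits the importance of the point. It does not make a one-sided shift part of the confidence interval.

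**Conclusion.** The point holds for the 9-month landmark. Counting 56-day intervals from first dose or randomization, nine months falls 3 to 9 days before any in-window Week 40 scan. Under exponential PFS the overstatement is about 6 to 7 points for medians of 3 to 12 months if all events are dated at scheduled scans. It is about 5 to 6.6 points at a 5.3-month median if 10 to 30% carry their own dates.

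Two stronger readings are not supported. One is that all three landmarks are materially biased: the 6- and 12-month effects are only about 3 points, and both dates already fall after the preceding scan window has closed. The other is that a Stage 2 clock starting at randomization pushes the scans later still: Section 4.6.3 treats randomization and Week 1 as one visit, with the first dose taken there.

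**What to change.** In the SAP:
1. State one time origin for PFS and TTP, reconciling Section 6.3.4 with Section 4.5.2. Define the month in days and state that scan weeks are elapsed weeks from Day 1.
2. Read the 9-month landmark just after the Week 40 window closes, for example at Week 41 (Day 287), and label it in weeks. Alternatively, keep the 9-month label and add an interval-censored estimate as a sensitivity analysis, with the interval running from the last progression-free scan to the scan showing progression and deaths taken as exact.
3. Keep the 6- and 12-month landmarks, with a footnote that they reflect the Week 24 and Week 48 scans. Moving them gains little: Week 25 returns the same scheduled-scan value as six months, and Week 57 (399 / 30.4375 = 13.1 months) would replace the 12-month estimate with a later one.
4. Apply the same rules to TTP and to PFS by modified RANO.

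The cost is SAP wording and a few lines of code, with no change to visits or sample size. The downside is a lower 9-month rate or a landmark labelled in weeks. At a 5.3-month median with all events at scheduled scans, the Week 41 reading would be 0.5^(9.20/5.3) = 30.0%, against 38.2% as now planned. Scans taken outside the 3-day window, including those in off-treatment follow-up, could still fall after Week 41.
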